2.3.2 Procedural endpoints

- 1) Procedural safety
- 2) Procedure time to FFR
- 3) Procedure time to QFR
- 4) Time to QFR after receiving angiographic images
- 5) Contrast use
- 6) Fluoroscopy time

2.4 Study procedure

[figure not shown]
2.4.1 Enrollment and angiographic based exclusion

Patients fulfilling clinical inclusion criteria and fulfills no clinical exclusion criteria are enrolled by providing written informed consent before the procedure (see section 6.3). During angiography patients enters the QFR cohort if fulfilling angiographic inclusion criteria. If patients have angiographic exclusion criteria, they are excluded before attempting QFR. All enrolled patients are entered in the study eCRF. If excluded, reasons are entered in the eCRF.

2.4.2 Study procedure flow

The CAG procedure with FFR assessment is performed as normal best practice. QFR is calculated for all the vessels in which FFR assessment is planned. Angiographic projections are acquired

ensuring minimal overlap of the investigated vessels. Two projections of each vessel to be assessed are obtained at least 25 degrees apart. After initial diagnostic angiography the images are transferred to a workstation for calculation of the QFR-value. Not awaiting the result hereof, the operator continues the procedure by measuring standard FFR during I.V. hyperaemia. The FFR trace is recorded from before inducing hyperaemia to verification of drift not exceeding prespecified limits (section 2.4.3). The procedure is finalized as by normal practice according to the results of angiography and standard FFR. The QFR value is calculated in parallel and the results noted before knowing the measured FFR values. The QFR value may not be used for diagnosing the patient.

2.4.2.1 Coronary angiography, detailed

Two good projections at least 25 degrees apart are required for the 3D vessel reconstruction.

Angiographic procedure:

- Inject I.C. nitro-glycerine as early as possible
- Use framerate of at least 12.5/15 frames/sec
- Make sure that the catheter is filled with contrast before the injection (i.e. after administration of nitro-glycerine)
- Use brisk, continuous and fast contrast injections. Aim for full 3 cardiac cycles

- Minimize overlap of target segments
- Avoid foreshortening of the vessel
- Avoid zooming
- Avoid moving the table early after injection
- Aim projections perpendicular to the target vessel
- Make sure that the entire vessel is visible in both projections. Both the proximal end and the potential position of the FFR pressure transducer should be visible in the same frame.

Suggested projections are found in table 1.

Vessel /Bifurcation	1st View	2nd View
LM + LAD/LCX	RAO 20, Caudal 45	AP, Caudal 10
LAD/Diag	AP, Cranial 45	RAO 35, Cranial 20
LCX/OM	LAO 10, Caudal 25	RAO 25, Caudal 25
Proximal+Mid RCA	LAO 45, CAUD 0	AP, CAUD 0
PLA/PDA	LAO 45, CAUD 0	LAO 30, CAUD 30

If only one good projection is identified, consider to use the *Acquisition Guide* tool in the Medis Suite QAngio XA 3D/QFR solution to identify the second projection:

1. Transfer first good projection to QFR computer (see section 2.4.2.2).
2. Right-click on the good projection and start QAngio3D.
3. Choose *Acquisition Guide* (**Figure 1**, red box). The yellow line on the angiography indicates the new projection angle, and should be approximately perpendicular to the target vessel at the lesion site.
 - a. If several lesions are located on the same vessel, a compromise must be made to ensure that most and the most severe lesions can be seen in the same projection.
4. Move the projection line by moving the yellow spot (**Figure 1**, arrow) in the Acquisition Guide indicator. Aim to keep the yellow spot inside the green area.
5. Position the C-arm as proposed by the guide.
6. In case of excessive overlap of the target segments and other vessels, rotate the C-arm 5 degrees around the axis of the target vessel.

a. If needed, use the Acquisition guide indicator again by maintaining the angulation of the yellow line and move the yellow spot just outside the green area – away from the red area. Move the C-arm accordingly.

[figure not shown]

Figure 1 Acquisition Guide. Red box: Acquisition guide. White arrow: Yellow spot indicating position of C-arm.

2.4.2.2 Image transfer

The angiographic runs are transferred to the QFR-computer using an angiographic equipment specific protocol.

2.4.2.3 Angiographic run selection

Optimal projections are chosen according to the following criteria:

- Minimal overlap of the target vessel
- Good contrast injection, filling the entire vessel
- Includes both most proximal stenosis and most distal potential location of the pressure transducer of the subsequent FFR assessment

2.4.3 Detailed description of FFR recording:

The pressure wire is prepared and calibrated according to instructions for use. The pressure wire is advanced in the engaged guiding catheter and the pressure transducer positioned just outside the

tip of the catheter and equalized. After equalization, the wire is advanced to a position with the transducer in a stable position distal to the stenosis. In case of long healthy segments distal to the lesion, do not advance the FFR wire to a very distal position as this increases the complexity of acquiring appropriate angiographic views.

I.V. FFR recording: Recording of FFR during I.V. adenosine induced hyperemia is performed by femoral or brachial vein infusion of adenosine at $140 \mu\text{g L}^{-1}\text{min}^{-1}$. The infusion rate is increased to $200 \mu\text{g L}^{-1}\text{min}^{-1}$ if a stable FFR value is not achieved. At least 20 seconds of the lowest stable value is documented before obtaining an angiographic projection during hyperemia, which should at least be 25 frames/sec.

The entire FFR interrogation is recorded from before equalization and until a potential drift has been checked after retracting the pressure wire.

FFR is calculated as the ratio of distal mean pressure (Pd) measured by the pressure-wire to the proximal mean pressure (Pa) during hyperemia. The FFR cut-off for identification of a flow limiting stenosis is ≤ 0.80 for all lesions. The wire location is documented angiographically for all measurements. A pressure-wire pullback is performed to check for pressure-drift. A drift-value from 0.96-1.04 is accepted; otherwise, the procedure is repeated. For FFR values of 0.76-0.84, a drift with a narrower range of 0.98-1.02 is accepted.

St. Jude FFR systems are recommended, but Volcano FFR systems can be used as well. iFR recordings and Acists FFR system are not allowed. It is mandatory that complete FFR traces can be exported for documentation and core lab analysis. If using the St. Jude Quantien system it is crucial to finalize the recordings and session correctly on the console to avoid loss of FFR data. FFR systems integrated in physiology systems or angiographic equipment are only allowed if a complete trace can be reanalyzed by the FFR core laboratory.

2.4.4 Detailed description of QFR computation

The Medis Suite QAngio XA-3D/QFR solution (Medis medical imaging system bv, Leiden, The Netherlands) is used for computation of QFR. The Medis Suite QAngio XA-3D/QFR solution is installed on a windows based computer. The analysis is performed as described in the manual provided with the software and in a step-by-step study specific standard operating procedure (Appendix A)

2.4.4.1 Documentation of QFR analysis

After finishing the QFR analysis, it is saved by two steps for the study purpose.

1. A screenshot is acquired and saved in a folder named "Patient X", X indicating the patient's study ID.
2. The QFR analysis is saved in the Medis Suite QAngio XA 3D/QFR solution by clicking *Done* in the lower right corner (**Figure 2**, white arrow) and clicking *Save* in the upper panel (**Figure 2**, red arrow).

[figure not shown]

Figure 2 Documentation. How to save the analysis in the Medis Suite QAngio 3D-/QFR solution.

After a session is made and saved, Medis Suite QAngio XA 3D/QFR solution will create a Report (summarizing the analysis, including 2D images of the vessel reconstruction, the 3D reconstruction, results etc.). You can easily change which parts of the analysis the report includes by clicking on the different parameters (**Figure 3**, left panel).

[figure not shown]

Figure 3 Report

2.4.5 Endpoint definition

2.4.5.1 Feasibility

Fraction of lesions with FFR where QFR was computed

Time to QFR: Time from first image evaluation on QFR computer until TIMI frame count based QFR is obtained.

Time to FFR: Time from starting preparations to do FFR (e.g. ordering assistants to prepare pressure wire, adenosine infusion) FFR value is obtained AND drift has been verified to be within the prespecified limits

2.4.5.2 Endpoint definitions: 3D Quantitative Coronary Angiography (3D-QCA)

- Percentual diameter stenosis: (Reference diameter \div minimal luminal diameter)/reference diameter in percent

2.4.6 Definitions of clinical endpoints (procedural)

2.4.6.1 Cardiac death

Encompasses death due to coronary heart disease including fatal myocardial infarction, sudden cardiac death including fatal arrhythmias and cardiac arrest without successful resuscitation, death from heart failure including cardiogenic shock, and death related to a cardiac procedure or surgery within 28 days from the procedure. If death is not clearly attributable to other non-cardiac causes, it will be adjudicated as cardiac death.

2.4.6.2 All-cause mortality (total death)

Total death includes cardiac death and other fatal categories such as cerebrovascular death, death from other cardiovascular disease (i.e. pulmonary embolism, dissection aortic aneurism will be included in this category), death from malignant disease, death from suicide, violence or accident, or death from other reasons.

2.4.6.3 Non-procedure related target lesion myocardial infarction

The term myocardial infarction should be used when there is evidence of myocardial necrosis in a clinical setting consistent with myocardial ischemia. Under these conditions any one of the following criteria meets the diagnosis for myocardial infarction:

- 1) Detection of rise and/or fall of cardiac biomarkers (preferably troponin) with at least one value above the 99th percentile of the upper reference limit (URL) together with evidence of myocardial ischemia with at least one of the following (MI types 1 or 2):
 - a. Symptoms of ischemia
 - b. ECG changes indicative of new ischemia (new ST-T changes or new LBBB)
 - c. Development of pathological Q waves in the ECG
 - d. Imaging evidence of new loss of viable myocardium or new regional wall motion abnormality
- 2) Sudden, unexpected cardiac death, involving cardiac arrest, often with symptoms suggestive of myocardial ischemia, and accompanied by presumably new ST elevation, or new LBBB, and/or evidence of fresh thrombus by coronary angiography and/or at autopsy, but death occurring before blood samples could be obtained, or at a time before the appearance of cardiac biomarkers in the blood (MI type 3).

3) Pathological findings of an acute myocardial infarction.

2.4.6.4 Procedure related biochemical release of markers (Myocardial infarction related to the index procedure)

The following biomarkers may be used in the study: CK-MB mass and/or Troponin-T/-I. For percutaneous coronary interventions (PCI) in patients with normal baseline biomarker values, elevations of CK-MB greater than 5 X 99th percentile URL are designated as defining PCI-related myocardial infarction (MI type 4a). Similar rise or higher by TnT or TnI will be reported. If cardiac biomarkers are elevated before the procedure and not stable for at least two samples 6 hours apart, there are insufficient data to recommend biomarker criteria for the diagnosis of peri-procedural myocardial infarction. If the values are stable or falling, criteria for re-infarction by further measurement of biomarkers can be applied; that is 20% or more increase of the value in the second sample after the procedure. This value should also exceed the 99th percentile URL.

2.4.6.5 Target lesion revascularization

Coronary artery bypass grafting or PCI of index lesion.

2.4.6.6 Target vessel revascularization

Coronary artery bypass grafting or PCI of index vessel.

2.4.6.7 Target lesion failure

Target lesion failure is defined as objective evidence for in-segment occlusion (symptomatic or asymptomatic) or stenosis causing ischemia.

2.4.6.8 Target vessel failure

Target vessel failure is defined as objective evidence for in-vessel occlusion (symptomatic or asymptomatic) or stenosis causing ischemia.

2.4.6.9 Stent thrombosis

Stent thrombosis is recognized when documented by angiography and/or autopsy and when meeting the criteria for spontaneous myocardial infarction occurring in the territory of the treated vessel. Stent thrombosis is categorized as acute, sub-acute, late and very late and as definite, probable and possible according to the ARC-criteria⁸.

2.4.7 FFR core lab analysis

The recorded FFR traces are analyzed by experienced observers at the Coronary Physiology Core Laboratory, Aarhus University, Denmark. The observers are blinded to any other procedural information. FFR recordings are analyzed for achievement of maximal hyperemia, no reversed gradient during hyperemia, no loss of Pa or Pd signal and acceptable drift.

2.4.8 QFR core lab

The angiograms are reanalyzed by two observers blinded to any procedural results and FFR results. Analysis is performed using the three flow models; fixed hyperemic flow rate (HFR), TIMI flow based without hyperaemia and TIMI flow based with hyperaemia. Analysis is performed applying same principles as during on-line computation. Analysis is performed at the core laboratory for interventional imaging at Aarhus University Hospital, Denmark

3. Statistics and sample size

3.1 Statistics

Baseline characteristics and procedural characteristics are presented as count and percentages, or if continuous variables are analyzed by mean and standard deviation if Gaussian distributed, else reported as medians and inter-quartile range. If more than one vessel is assessed per patient it is analysed on a per vessel level. Feasibility is calculated as the number of successful QFR/number of standard FFR times 100. The primary endpoint is calculated as superiority for sensitivity and specificity of QFR in comparison to QCA. The QCA value in analysis is the lesion site 3D QCA value obtained on-line during QFR analysis. Secondary endpoints include positive predictive value, negative predictive value, together with their 95% confidence intervals (CIs). The area under the curve by receiver-operating characteristic analysis is used to assess the diagnostic accuracy of QFR and QCA with FFR as gold standard. The diagnostic performance of QFR compared to 2D QCA is performed by one-tailed paired comparison of ROC curves (Hanley test). Pearson correlation is used to quantify the correlation between QFR and FFR. Agreement between QFR and FFR is assessed by Bland-Altman plot. Intra- and inter-patient variation in paired QFR and FFR values are compared to detect clustering. Analysis is performed using STATA 13.

3.2 Sample size

The study is an observational study designed to assess the diagnostic accuracy of QFR with FFR as gold standard. Estimates for the sample size calculation are based on the results from the FAVOR study, where a sensitivity of 0.74 and a specificity of 0.91 for QFR was found. The null hypothesis is H_0 : Sensitivity(QFR) = Sensitivity(DS50). H_1 : Unequal sensitivities for the two methods.

Calculated with SAS version 9.4 with proc power for paired frequency, to do a sample size analyses for McNemar's test for paired proportions.

We did a normal-approximate McNemar test with the Connor method;

Proportion1=0.48; proportion2=0.74; correlation=-0.1

We did similar for specificity (Ho: Specificity(QFR) = Specificity(DS50). H1: Unequal specificities for the two methods.

Proportion1=0.75; proportion2=0.91; correlation=0.4

With power=0.90, alpha=0.05 and a rate of true positives in the population of estimated 30% a total of 274 patients with paired QFR and FFR are required to reject the null hypothesis for sensitivity and 257 for specificity. To accommodate for insufficient angiographic quality or failed FFR a total of 310 patients should be enrolled.

4. Notifications

The study is notified to the Central Denmark Region Committees on Biomedical Research Ethics. Notification to local or national medical ethics committees is performed by the local or national coordinating investigators as required for the individual sites. The study is initiated center wise when full final approval is obtained covering the specific center.

The study does not require notification to the respective National Board of Health as the tested QFR technology is not in contact with the patient (simple file transfer from angiographic equipment to a standard personal computer (PC)) and the obtained measurements are not used for diagnosing the patient during, or at any point after the individual study procedures.

The study is notified to the Danish Data Protection Agency. Data is transferred to the Danish Data Archive before termination of the data controller permission and deletion of all the related study material at Aarhus University Hospital. Data is handled, processed and stored according to the regulations set forth in the "Persondataloven" and published guidelines by the Danish Data Protection Agency. Any additional use or transfer of data is only done pending permission by the Danish Data Protection Agency and by signed data processor agreement if applicable. The notification to the Danish Data Protection Agency covers the handling, processing, storage and transmission for all participating sites in all EC countries. All sites and investigators are required to obey the data protection regulations as referred to in the site contract. Sites outside the EC zone should obtain permission from local or national data protection authorities if required by law.

5. Data management

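### Section 3.2 states 257 patients for specificity; its own inputs give 110, and 257 matches dividing by the FFR-positive rate (30%) instead of the FFR-negative rate (70%)

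*Combined protocol and SAP*

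**What the plan says.** Section 3.2 (Sample size) describes two paired comparisons of QFR with the 50% diameter-stenosis criterion (DS50), one for sensitivity and one for specificity.

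- Method: "We did a normal-approximate McNemar test with the Connor method".
- Sensitivity inputs: "Proportion1=0.48; proportion2=0.74; correlation=-0.1".
- Specificity inputs: "Proportion1=0.75; proportion2=0.91; correlation=0.4".
- Alternative hypothesis for specificity, which makes the test two-sided: "H1: Unequal specificities for the two methods". Sensitivity is worded the same way.
- Error rates and case mix: "With power=0.90, alpha=0.05 and a rate of true positives in the population of estimated 30" per cent.
- Result: "a total of 274 patients with paired QFR and FFR are required to reject the null hypothesis for sensitivity and 257 for specificity".
- Enrolment: "To accommodate for insufficient angiographic quality or failed FFR a total of 310 patients should be enrolled".

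The step from the number of informative cases to the total number of patients is not shown. No FFR-negative rate is given; 70% follows as the complement of 30%. Sections 1.2, 2.3.1.1 and 3.1 make sensitivity and specificity together the primary hypothesis and endpoint.

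**The concern.** Sensitivity is estimated only in cases that are positive by FFR, and specificity only in cases that are negative by FFR. When 30% of cases are positive, negatives are more than twice as common, so a given number of negatives needs far fewer patients in total. The two printed totals are nevertheless nearly equal, although the two tests need similar numbers of informative cases. That suggests the same divisor was used for both.

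The stake is how the design is read, not the number enrolled. Printed as 274 and 257, the two halves of the primary endpoint look about equally demanding and equally at risk. If they are not, a reader misjudges which assumption matters most and how likely the study is to succeed on both.

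**Working it through.** **Inputs** (all from section 3.2): two-sided alpha 0.05, so z = 1.960; power 0.90, so z = 1.282; sensitivity 0.48 vs 0.74 with correlation -0.1; specificity 0.75 vs 0.91 with correlation 0.4; 30% FFR-positive, hence 70% FFR-negative.

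**Formulas** (Connor normal approximation for McNemar's test)

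- Both methods correct: p11 = p1·p2 + r·√[p1(1−p1)p2(1−p2)]
- Discordant proportion: ψ = (p1 − p11) + (p2 − p11); difference: d = p2 − p1
- Informative cases: n = [1.960·√ψ + 1.282·√(ψ − d²)]² / d²
- Total patients: n, rounded up, divided by the share of patients with the relevant FFR status

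**Sensitivity (reproduces the plan)**

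- ψ = 0.1467 + 0.4067 = 0.5534; d = 0.26; d² = 0.0676
- n = (1.960 × 0.7439 + 1.282 × 0.6970)² / 0.0676 = 81.8, so 82 FFR-positive cases
- 82 / 0.30 = 273.3, so **274**, as printed

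**Specificity**

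- ψ = 0.0179 + 0.1779 = 0.1959 (cells rounded for display); d = 0.16; d² = 0.0256
- n = (1.960 × 0.4426 + 1.282 × 0.4126)² / 0.0256 = 76.15, so 77 FFR-negative cases
- 77 / 0.30 = 256.7, so **257**: the printed figure, reached only with the FFR-positive rate as divisor
- 77 / 0.70 = **110**: the figure that follows from the stated inputs
- 257 / 110 = 2.3

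**Could 257 be right on another reading?**

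- A total of 274 for sensitivity needs an FFR-positive rate of about 0.30. A total of 257 for specificity needs an FFR-negative rate of about 0.30, that is, an FFR-positive rate of about 0.70. At 0.70, sensitivity would need 82 / 0.70 = 117.1, so 118. No single rate gives both printed totals.
- With the 0.70 divisor, other versions of the test do not reach 257 either: Connor one-sided 89; Connor two-sided with a 1/d continuity correction 119; Miettinen two-sided 89; Miettinen one-sided 70.

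**Power at 274 paired patients**, from power = Φ{[d·√n − 1.960·√ψ] / √(ψ − d²)}

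| Test | Informative cases | Power |
|---|---|---|
| Sensitivity | 0.30 × 274 = 82.2 | 90.1% |
| Specificity, 70% negative | 0.70 × 274 = 191.8 | 99.9% |
| Specificity, if 257 were right (30% negative) | 0.30 × 274 = 82.2 | 92.1% |

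The two tests use separate groups of cases. Treating them as independent, joint power is 0.901 × 0.999 = 90%. Had 257 been right, it would be 0.901 × 0.921 = 83%.

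**Where the risk lies.** As an illustration, suppose 25% of patients were FFR-positive instead of 30%. Then 0.25 × 274 = 68.5 positives give 84% power for sensitivity, while specificity stays above 99.9%.

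**The case against.** The strongest reply is that nothing in the design depends on the figure. Sensitivity needs 274 whether specificity needs 257 or 110, and the 310 to enrol is built on 274. The error overstates a requirement that does not bind, so no patient is added, lost or exposed. This stands, and it caps the importance of the point.

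Three narrower objections also have some force.

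- The plan does not print the division, so the wrong divisor is inferred. That is true, but one method, one rounding rule and one divisor reproduce both printed totals exactly. That 257 does not follow from the stated inputs needs no inference about how it arose.
- The plan states no joint power. The 83% and 90% are derived here and show only what a reader could infer.
- The value of 110 depends on the planning inputs, especially the correlation of 0.4. At correlation 0 the formula gives 117 negatives (117/0.70 = 167.1, so 168 patients). At -0.1, the value used for sensitivity, it gives 128 (128/0.70 = 182.9, so 183). The calculation also takes one independent unit per patient, whereas section 3.1 analyses per vessel. Dividing before rounding gives 109 instead of 110, although the printed 257 shows that the plan rounded first.

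None of these recovers 257.

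**Conclusion.** The concern holds. On the plan's own inputs, the specificity comparison needs 110 patients with paired measurements, not 257. The printed figure is too high by a factor of 2.3 and cannot be reconciled with the 274 printed beside it under any one FFR-positive rate.

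The consequence is limited to how the design is described: 274 and 310 are unaffected. What changes is the reading of the primary endpoint. At 274, specificity has very high power and sensitivity only just meets its 90% target, so success on both depends almost entirely on the number of FFR-positive cases. These power figures assume the stated proportions and correlations, 30% FFR-positive and one independent unit per patient; the joint figure also assumes that the two tests are independent. This should be corrected, but it does not put the study at risk.

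**What to change.** In section 3.2:

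- Replace the specificity total of 257 with 110, and show both divisions: 82 FFR-positive cases / 0.30 = 274, and 77 FFR-negative cases / 0.70 = 110.
- Add that, under the planning inputs, 274 paired patients give about 90% power for sensitivity, more than 99% for specificity and about 90% for both, with the two tests taken as independent.
- Replace "a rate of true positives in the population of estimated 30" per cent with wording that names it as the FFR-positive rate. A true positive normally means positive by both the test and the reference, which is not what the calculation uses.
- Keep 274 and 310.

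The cost is a short text edit. No patient number, procedure or analysis changes.
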